5.8 Treatment

CHRONOS-A

- Arm 1 (Control arm): Radical therapy (prostatectomy or radiotherapy [external beam or brachytherapy]). The type of radical therapy will be determined by physician or patient preference.
 - In radiotherapy patients, neoadjuvant ADT permitted and if given, minimum 3 months and maximum 6 months duration.
 - We anticipate lymph node treatment in this group is not required but 'for cause lymph node treatment will be permissible if strong clinical preference is demonstrated.
 - If an extended lymph node dissection is anticipated this will need to be discussed in a central review by the surgery subgroup.
 - As per Radiotherapy Trials Quality Assurance (RTTQA) centres and physicians delivering radiotherapy will need to be approved.
 - o Radiotherapy detailed protocols will be set out in a separate SOP.
 - Surgeons and surgical centres currently are approved as a national commissioning programme so any centre or surgeon permitted to carry out radical prostatectomy in standard NHS practice will be permitted to deliver prostatectomy within this trial.
 - o Prostatectomy details will be set out in a separate SOP.
- Arm 2 (Intervention arm): Focal therapy alone (high intensity focused ultrasound [HIFU] or cryotherapy or other validated energy modality as per physician/patient decision/choice. Other energy modality will only be added after TSC and TMG approval and a substantial amendment approved by all required bodies.
 - A second treatment either in-field or out-of-field will be permitted either after the MRI and optional biopsy showing clinically significant cancer at 12-months or due to suspicion of residual or new contralateral disease at a future date with a positive biopsy for clinically significant cancer.
 - Cryotherapy can be used after HIFU and HIFU can be used after cryotherapy.
 This second focal therapy session will be part of the focal therapy intervention
 - Where patients have undergone hemiablation to one lobe and then undergo hemiablation of the contralateral lobe will be designated as failure of focal therapy
 - Focal therapy details will be set out in a separate SOP.

Patients previously or currently on 5 alpha reductase inhibitors or anti-androgens, or LHRH agonists or LHRH antagonists are still eligible for CHRONOS A.

CHRONOS-B

 Arm 1 (Control arm): Focal therapy alone (high intensity focused ultrasound [HIFU] or cryotherapy or other validated energy modality as per physician and centre choice). A second treatment in-field, or a first focal ablation to an out-of-field progressive or de novo lesion will be allowed but will be regarded as failure events for the purpose of CHRONOS-B. Cryotherapy can be used after HIFU and HIFU can be used after

Short Title: IP4 - CHRONOS	Protocol No: 19CX5006	Sponsor: Imperial College London	Version: 5.0 Date: 13 th July 2022
			10 daily 2022

cryotherapy. Where patients have undergone hemiablation to one lobe and then undergo hemiablation of the contralateral lobe will be designated as failure of focal therapy

- Arm 2 (Intervention arm): Neoadjuvant finasteride 5mg once daily for a minimum of 12 weeks (84 days) followed by focal therapy (as per control arm).
- Arm 3 (Intervention arm): Neoadjuvant bicalutamide 50mg once daily therapy for 12 weeks (84 days) followed by focal therapy (as per control arm).

Other arms can be added in future with protocol amendments.

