To date, approximately 90% of FT cases in the UK are intermediate or low-volume high-risk cancers. There is currently no evidence comparing FT to standard of care active treatments such as radiotherapy or prostatectomy in men with clinically significant cancer. A recently completed pilot RCT comparing FT to prostatectomy (called PART) had a feasibility objective to meet a recruitment rate of 50% of men approached. However, after screening 356, 244 were eligible, of whom only 70 men accepted randomisation. 20% of those randomised to prostatectomy refused their allocation, but none declined in the FT arm. We previously reviewed 12 RCTs in which very different interventions in localised prostate cancer were compared, but failed to accrue. We proposed that there was a need to ensure novel trial designs that embrace clinical and patient equipoise [16].

In addition to the need for RCTs comparing FT against standard care with radical radiotherapy/prostatectomy, there clearly needs to be a deeper understanding as to why failure occurs after FT and to develop strategies to reduce the need for further treatment. Failure can occur due to, a) heat-sink effects countering thermal effects, b) swelling during treatment causing skip-lesions or, c) progressive/de-novo out-of-field development of significant cancers. Strategies that decrease neovasculature, reduce tumour volume, or potentiate the immune response induced by ablation might complement FT to reduce failure [16-28]).

If FT fails it can be redone to the same area; an attribute that is missing from radical therapies. If redo FT fails, then men can still proceed to radical therapy. Over a 5-year median follow-up, redo FT rates are approximately 20-30% and salvage radical or systemic therapy occurs in 10%. Metastases are uncommon (3%) and cancer-specific survival 100% over the same period of time [10]. By comparison, the reported failure rate requiring further treatment after radical therapy is about 10-20% over a 5-10 years median follow-up. Currently 4-5% of cases have out-of-field failure at a median of 5 years [29], which might represent progression or may represent the false-negative rates of mpMRI and biopsy used to localise disease prior to focal therapy. Although many patients accept these rates of further treatments after FT, there is a need to investigate strategies that might optimise FT further to reduce patient and healthcare burden.

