2.2 Main Study Primary Objectives

CHRONOS-A

To evaluate progression-free survival (PFS) rates of focal therapy alone compared to radical therapy (radiotherapy or surgery) in the treatment of non-metastatic clinically significant prostate cancer. PFS is defined as time from randomisation to salvage whole-gland or systemic therapy, prostate cancer metastases or prostate cancer-specific mortality.

CHRONOS-B

Short Title: IP4 - CHRONOS	Protocol No: 19CX5006	Sponsor: Imperial College London	Version: 5.0 Date: 13 th July 2022
			-

• To evaluate Failure-Free-Survival (FFS) rates of focal therapy alone compared to focal therapy combined with other therapies as a neoadjuvant strategy. FFS is defined as time from randomisation to further focal therapy session or salvage whole-gland or systemic therapy or prostate cancer metastases or prostate cancer-specific mortality.

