2.5 Main Study Primary Endpoints

CHRONOS-A

Progression-Free Survival (PFS) with progression defined as biochemical failure (radical therapies only), salvage therapy (local or systemic) or prostate cancer metastases or prostate cancer specific mortality. Salvage local therapy following focal therapy will be defined as surgery or radiotherapy or 3 or more focal therapy sessions. Any radiotherapy given after prostatectomy will be counted as an event.

CHRONOS-B

Failure-Free survival (FFS) with failure defined as time to one further focal therapy session or salvage therapy (local radiotherapy or surgery, or systemic) or prostate cancer metastases or prostate cancer specific mortality.

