- As there is no defined time-point for a PSA nadir value following FT the PSA value at 12-months post randomisation in patients with a negative MRI will be used. Following this if there are any two further consecutive rises in PSA at least 3 months apart, with no influencing factors at the time (e.g., urinary tract infection, instrumentation/procedures, biopsies, catheterisation), a for-cause mpMRI with or without biopsies can be carried out at the discretion of the treating clinician. The Focal Therapy Sub-Group should be informed of this and a review of the for-cause mpMRI findings prior to biopsy should be carried out. Clinically significant prostate cancer in-field that is suitable for further FT should be offered to patients as a routine. Radical therapy should be only recommended to patients in instances where further FT is not suitable. Such situations should only occur after the Focal Therapy Subgroup has reviewed the case as expertise for such decisions may not reside in the local centre.
- In CHRONOS A, a second treatment either in-field or out-of-field will not be classified as failure and is part of the overall focal therapy intervention. In patients who undergo a second treatment of FT the nadir value will be defined at the 12-month time point after the second treatment, provided mpMRI and biopsy targeted at treated area(s) are negative for clinically significant prostate cancer.

Radiotherapy/ Brachytherapy

 In patients where there is suspected PSA relapse but the international definition of biochemical failure (PSA nadir plus 2.0ng/ml) has not been reached, evaluation should include a for-cause mpMRI and biopsy if required. Staging scans should be done as

Short Title: IP4 - CHRONOS	Protocol No: 19CX5006	Sponsor: Imperial College London	Version: 5.0 Date: 13 th July 2022
			10 daily 2022

per local practice. Where salvage local or systemic therapy is given, this will be regarded as PFS event.

Surgery

- Adjuvant or salvage radiotherapy will be regarded as a PFS event and will be determined based on histological findings and PSA kinetics even if the biochemical failure definition is not reached (PSA >/=0.2ng/ml). Staging scans should be done as per local practice.
- Biochemical failure following radical therapy as internationally defined, even if salvage therapy is not given, will be counted as an event for PFS/FFS analyses.

Collection of postcodes

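### CHRONOS-A focal arm: section 5.8 calls a contralateral hemiablation a failure, sections 5.9 and 2.5 do not, so its PFS event status is left open

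*Protocol*

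**What the plan says.** Protocol 5.8 (CHRONOS-A, Arm 2) permits a second focal session, in-field or out-of-field. One of the permitted grounds is a session "due to suspicion of residual or new contralateral disease at a future date with a positive biopsy for clinically significant cancer". The section then adds: "This second focal therapy session will be part of the focal therapy intervention". The next bullet says that men who have had hemiablation of one lobe and then "undergo hemiablation of the contralateral lobe will be designated as failure of focal therapy".

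Protocol 5.9, under its heading on tests and definitions of failure, says that in CHRONOS-A "a second treatment either in-field or out-of-field will not be classified as failure and is part of the overall focal therapy intervention".

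Protocol 2.5, which defines the primary endpoint, says: "Salvage local therapy following focal therapy will be defined as surgery or radiotherapy or 3 or more focal therapy sessions". Section 2.2 words the endpoint differently: "PFS is defined as time from randomisation to salvage whole-gland or systemic therapy", or metastases or death from prostate cancer. Neither section mentions hemiablation.

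The trial summary treats a first session to an out-of-field lesion as part of the CHRONOS-A focal intervention. SAP 6.2.1 also treats the second session as part of the intervention and leaves out the hemiablation sentence. The SAP covers the feasibility stage only and defines no PFS events.

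The same hemiablation sentence appears in 5.8 for the CHRONOS-B control arm, where any second focal session is already a failure event.

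**The concern.** A man who has a right hemiablation and later a left one has had two focal sessions, the second outside the first field. Whether he has failed depends on which section is read. If the failure in 5.8 is meant to feed PFS, the primary-event rule has two answers for him.

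The ambiguity cannot balance between arms, because only focal-arm men can have this sequence. The trial is open-label (5.4), so anyone settling the question later would know the allocation. The comparison is a non-inferiority test with a 5-point margin (8.1.2), so a small shift in one arm's event rate uses a visible part of the margin. Pilot patients carry into the main stage (8.1.1), so some men may be followed before the rule is settled.

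**Working it through.** **The text, applied to one man with two sessions (one lobe, then the other)**

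| Place | Result for this man |
|---|---|
| 5.8, hemiablation bullet | Failure of focal therapy |
| 5.8, preceding bullets | Second session permitted, part of the intervention |
| 5.9 | Not a failure; no exception stated |
| 2.5 | Not salvage (two sessions, threshold three) |
| 2.2 | Unclear: depends on whether two hemiablations amount to whole-gland salvage |
| Trial summary, SAP 6.2.1 | Part of the intervention |

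The conflict between 5.8 and 5.9 needs no arithmetic. The rest of this field only sizes it.

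**Inputs.** Control PFS 0.85, margin 0.05, power 0.80, alpha 0.05 (sidedness not stated), drop-out 5%, 1190 men and 136 events (8.1.2); 595 per arm (3.2); out-of-field failure 4-5% at a median of 5 years (1.1).

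**The plan's own figure.** For a two-proportion non-inferiority test with both arms at 0.85:

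n per arm = (z for alpha + z for power)² × 2 × 0.85 × 0.15 / 0.05²

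At one-sided 0.05 this is (1.645 + 0.842)² × 0.255 / 0.0025 = 631, or 1262 in total, and 1262 / 0.95 = 1329 with drop-out. At one-sided 0.025 it is 1602, or 1687 with drop-out. On the hazard scale the margin is ln 0.80 / ln 0.85 = 1.373, which needs about 247 events (one-sided 0.05) or 313 (one-sided 0.025) by Schoenfeld's formula. None of these matches 1190 and 136. That is a separate matter and does not bear on the contradiction, but it means the starting power below is not the plan's 80%.

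**Ceiling on the men affected.** 0.04 × 595 = 24 and 0.05 × 595 = 30. This treats every out-of-field failure as a contralateral hemiablation after an earlier hemiablation, with no other PFS event. The true share is not given.

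**Illustration.** Let x be the share of the focal arm counted as events only because of the 5.8 sentence. Focal PFS is then 0.85 − x. With n = 1190 × 0.95 / 2 = 565 per arm:

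SE = √[(0.85 × 0.15 + (0.85 − x)(0.15 + x)) / n]

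Chance of showing non-inferiority = Φ((0.05 − x) / SE − z for alpha)

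Example, x = 0.01: SE = √[(0.1275 + 0.1344) / 565] = 0.0215; 0.04 / 0.0215 − 1.645 = 0.21; Φ = 0.58.

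| x | Extra events in 595 | Share of margin | One-sided 0.05 | One-sided 0.025 |
|---|---|---|---|---|
| 0 | 0 | 0% | 76% | 65% |
| 1 point | 6 | 20% | 58% | 46% |
| 2 points | 12 | 40% | 39% | 28% |
| 4 points | 24 | 80% | 12% | 7% |

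The last row is close to the ceiling and should not be read as an expected case.

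**The case against.** The strongest reply is that 5.8 is a treatment section and never says that a contralateral hemiablation is a PFS event. Where the protocol means an endpoint event it says so: 5.9 names PFS for adjuvant or salvage radiotherapy after surgery, and 5.8 ties second sessions in CHRONOS-B to that trial's failure events. On the endpoint section alone, two focal sessions are not an event. This stands. A reader might infer that the protocol makes the same man both a PFS event and not one; the documents do not go that far. What remains is that 5.9 uses the same word, failure, for the same arm under a heading that defines failure, and denies it without exception. The protocol also gives the 5.8 designation no other stated use in CHRONOS-A.

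Second, the sentence can be harmonised. It may be a deliberate exception, since two hemiablations treat both lobes and 2.2 speaks of whole-gland salvage. Or it may have been carried over from CHRONOS-B, where it fits. Either is plausible. Neither is stated, and they lead to opposite classifications.

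Third, the size is uncertain. The 4-5% includes men who go on to surgery, radiotherapy or systemic therapy and would be PFS events anyway, and men whose out-of-field lesion is not treated by a second hemiablation. The planned analysis is an adjusted Cox model, not a two-proportion test. These points stand and limit the table to an illustration.

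Fourth, a reader might infer that non-inferiority logic obliges the sponsor to count these men as events because that is conservative. The documents do not support imposing it: 5.9, the trial summary and SAP 6.2.1 all treat the second session as part of the intervention under test, and the table shows that the choice may cost appreciable power.

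Finally, the main stage depends on funding and no PFS analysis is imminent. That leaves time to correct the text; it does not make the text consistent.

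**Conclusion.** The inconsistency is real: 5.8 and 5.9 classify the same second session differently, 2.5 contains no matching exception, and the feasibility SAP does not settle it. Its effect on PFS is an inference, though a reasonable one. It is confined to the focal arm. At most about 24 to 30 of 595 men would be affected if the 4-5% rate carries over, and probably fewer. On the stated assumptions (both arms otherwise at 85%, 565 evaluable per arm, one-sided alpha 0.05), reclassifying even 1% of the arm uses a fifth of the margin and lowers the chance of showing non-inferiority from about 76% to 58%. The documents do not show which reading is intended, and this review does not choose one. It should be settled before main-stage outcome data are reviewed.

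**What to change.** State once, in 2.5, whether hemiablation of one lobe followed by hemiablation of the other is a CHRONOS-A PFS event, and edit 5.8 and 5.9 to agree. Prespecify the other reading as a sensitivity analysis of the primary non-inferiority comparison. The sponsor chooses the primary reading. If it counts these men as events, the CHRONOS-A power assumptions should be checked against that choice. The change concerns outcome classification only, not who may be re-treated.

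Cost: one sentence, matching edits and one additional sensitivity analysis, plus the power check if the men are counted as events.

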5.9 Follow-up

Follow-up will consist of serum Prostate Specific Antigen (PSA) tests at 3 months and 12 months after completion of treatment as defined above. Thereafter, PSA will be measured 6-monthly until a progression event is determined, for 5 years after initial randomisation or mortality (whichever is first).

Patient reported outcome measures (PROMs) will be collected at 3 and 12 months and then annually thereafter until progression, mortality or 5 years after initial randomisation (whichever is first). The minimum follow-up for each patient will be 5 years in the main study although yearly follow-up will continue long term in clinical standard care through linkage to national databases.

NB: if the trial does not proceed to the Main Stage following the analysis of the Pilot, patients will be followed up for a minimum of 3 months and will then revert to standard of care in which the clinical care provided to patients will not differ from the clinical follow-up stipulated in this protocol. At the end of the study patients will continue to be followed up locally within their recruitment centres within the ICE (European Registry for Cryosurgical Ablation of the prostate, EuCAP) or the HEAT international HIFU registry as per NICE guidelines IPG432/IPG42.

Patient reported outcome measures

The EORTC QLQ-C30 with the prostate-specific module, International Prostatic Symptoms Score (IPSS), EPIC bowel and bladder and International Index of Erectile Function 15 (IIEF15) will be used.

The EuroQol (EQ-5D) will be used in the study as a generic measure of health-related quality-of-life which can be linked to public preferences. These data will be used to calculate quality-adjusted life-years as part of a future health economic evaluation. Patients agreeing to return questionnaires on quality of life should continue to complete quality of life data for 5 years after randomisation. Questionnaires should be self-administered, although it is recommended that a key person (e.g. research nurse) at each centre be responsible for the data collection to optimise compliance and completeness of the data.

The patients should complete the quality of life and the resource use data questionnaires independently without discussion with friends or relatives and all questions should be answered. The member of the study team should check each questionnaire and query any missing or incorrect data with the patient. Checks should also take place for date and identifiers. Patients should be approached at appropriate visits to complete the questionnaires.

Follow-up consultations

Short Title: IP4 - CHRONOS	Protocol No: 19CX5006	Sponsor: Imperial College London	Version: 5.0 Date: 13 th July 2022
			-

Collection of data at each time point will be permissible via postal, electronic, telephone or face-to-face communication. Unless the patient requests face-to-face visits they will only require attendance for hospitals visits that are defined by the local hospitals follow-up protocol within standard care. In certain circumstances it may be appropriate to replace hospital visits with telephone or email consultations providing that it is still possible to collect all the necessary follow-up information. In order to maintain confidentiality during email consultations these episodes will be conducted via the local site practitioner's protected NHS email account. Such remote consultations are undertaken frequently in routine clinical care and in these instances, it is acceptable to perform appointments with telephone or email consultations providing the required blood results, such as PSA tests are available to the research team (can be performed at local hospital or GP practice as per patients request and the GP's discretion). In any instance the hospital will carry out these tests if the GP was to refuse. All necessary information required to complete the follow-up case report form (CRF) is still required. All details on the telehealth consultations must be recorded in the patients' notes.

Study Visits - specific tests and definitions of failure

Focal therapy

- A prostate mpMRI and an optional targeted transrectal or transperineal prostate biopsy of the treated area at 12 months after focal therapy in CHRONOS-A and CHRONOS-B. Biopsies of the untreated area should only occur if new areas of score 4 or 5 occur. Those men who did not have a diagnostic quality mpMRI compliant with national guidelines before focal therapy should have biopsies of treated and untreated areas, if this is done. A biopsy SOP will give detail the requirements of the biopsy.
- As there is no defined time-point for a PSA nadir value following FT the PSA value at 12-months post randomisation in patients with a negative MRI will be used. Following this if there are any two further consecutive rises in PSA at least 3 months apart, with no influencing factors at the time (e.g., urinary tract infection, instrumentation/procedures, biopsies, catheterisation), a for-cause mpMRI with or without biopsies can be carried out at the discretion of the treating clinician. The Focal Therapy Sub-Group should be informed of this and a review of the for-cause mpMRI findings prior to biopsy should be carried out. Clinically significant prostate cancer in-field that is suitable for further FT should be offered to patients as a routine. Radical therapy should be only recommended to patients in instances where further FT is not suitable. Such situations should only occur after the Focal Therapy Subgroup has reviewed the case as expertise for such decisions may not reside in the local centre.
- In CHRONOS A, a second treatment either in-field or out-of-field will not be classified as failure and is part of the overall focal therapy intervention. In patients who undergo a second treatment of FT the nadir value will be defined at the 12-month time point after the second treatment, provided mpMRI and biopsy targeted at treated area(s) are negative for clinically significant prostate cancer.

Radiotherapy/ Brachytherapy

 In patients where there is suspected PSA relapse but the international definition of biochemical failure (PSA nadir plus 2.0ng/ml) has not been reached, evaluation should include a for-cause mpMRI and biopsy if required. Staging scans should be done as

Short Title: IP4 - CHRONOS	Protocol No: 19CX5006	Sponsor: Imperial College London	Version: 5.0 Date: 13 th July 2022
			10 daily 2022

per local practice. Where salvage local or systemic therapy is given, this will be regarded as PFS event.

Surgery

- Adjuvant or salvage radiotherapy will be regarded as a PFS event and will be determined based on histological findings and PSA kinetics even if the biochemical failure definition is not reached (PSA >/=0.2ng/ml). Staging scans should be done as per local practice.
- Biochemical failure following radical therapy as internationally defined, even if salvage therapy is not given, will be counted as an event for PFS/FFS analyses.

Collection of postcodes

In order to get an area-based estimate of deprivation, the participants' postcodes will be converted into an Index of Multiple Deprivation (IMD) score. The IMD is the established index of deprivation for England Wales and has been adopted widely in studies across local and national government. Postcodes will not be stored in the InForm Database only IMD rank, which is based on detailed ward-level index of deprivation based on severe separate domains.

Prostate Specific Antigen (PSA)

Blood sample for PSA can be collected during a scheduled hospital visit or at a hospital local to the patient or at a community/primary care facility, whichever is more convenient for the patient provided the result is available to the research team.

Patient reported outcome measures (PROMS)

PROMS questionnaires can be completed or returned during a scheduled hospital visit or via post/electronic communication.

Further follow-up imaging

Follow-up imaging will not be protocol led, except after focal therapy at the 12 month post focal therapy time-point) but we recommend imaging to take place when there is suspicion of progression such as patients with a rising PSA (biochemical failure). The appropriate imaging will be chosen as per the local hospital resources and policies. We envisage that the majority will perform a combination of a prostate MRI, nuclear medicine bone scan, PET-CT/MRI, Whole body MRI or CT chest/abdomen/pelvis.

Further follow-up biopsies

Some patients will undergo further biopsies if there is a need to confirm disease progression after the 12 month follow-up visit following focal therapy.

Further interventions

Some patients will also undergo secondary non-cancer related procedures to manage adverse events from the therapy such as, but not limited to, transurethral resection of prostate, bladder neck incision, urethral dilatation, optical urethrotomy, male-sling or other continence procedures as well as penile implant surgery for impotence. Endoscopic tests or interventions of the lower bowel may also be required. These rates of interventions will be collected.

Future follow-up

Patients will be consented for their names to be linked to national registries for survival information such as NHS Information Centre/Office of National Statistics (ONS) in England/Wales and General Register Office in Scotland, Hospital Episode Statistics (HES).

Protocol No: 19CX5006 v5.0 13th July 2022

IP4 - CHRONOS 19CX5006 Imperial College London Date: 13 th July 2022	Short Title: IP4 - CHRONOS	Protocol No: 19CX5006	Sponsor: Imperial College London	
---	-------------------------------	--------------------------	-------------------------------------	--

Biochemical Failure

For the purposes of this trial, biochemical failure will be defined after surgery and radiotherapy/ brachytherapy as per standard care. Early adjuvant or salvage therapy can be given prior to biochemical failure if clinically determined through an MDT. These will count as events for purposes of PFS. Focal therapy does not have a validated definition for biochemical failure.

- Radiotherapy/ brachytherapy: PSA nadir plus 2ng/ml as per Phoenix definition
- Surgery PSA >/=0.2ng/ml at any time-point after surgery

Confirming biochemical failure

The timing and thus assessment of PSA needs to be considered because rises in PSA can occur due to non-cancer related causes such as after procedures, biopsies or urinary tract infection (UTIs). Confirmatory samples are needed in all cases of a rising PSA prior to assigning an outcome of biochemical failure. After biochemical failure is confirmed for the first time it need not be reported again.

In the case that the raised PSA value reaches the biochemical failure value, a second confirmatory PSA test should be performed after at least 1 week or after 4 weeks after the completion of treatment in cases of UTIs, procedures or biopsies. Biochemical failure is confirmed if the second value also confirms this. The date of biochemical failure should be provided as the date of the **first PSA** that fulfilled the definition for failure.

If salvage treatment does start before the trial definition of biochemical failure is met then report the closest PSA value prior to the treatment start date as the progression value.

